The project is a randomized controlled study of smartphone based cardiac rehabilitation program compared to routine care in patients who did not sign up for traditional hospital-based cardiac rehabilitation. 50 patients who are randomized to the intervention group (mHealth) will be enabled with remote monitoring devices (Blood Pressure and wearable vital signs monitor, Biovotion) and “Kardia” mobile application, for home-based rehabilitation program followed by review in the outpatient Cardiology clinics. The control group (50 patients) will just be monitored at fixed intervals

in the outpatient Cardiology clinics. For drop out subjects, there will not be any subject replacement. See Figure below.

Cardiac Rehabilitation program

Patients will be advised to commence the exercise program 2 weeks after the myocardial infarction

Time	Exercise Intensity	Exercise Frequency/Duration	Patient actions
Week 1	light	3x/week; 10 minutes	Exercise diary
Week 2	light	3x/week; 20 minutes	
Week 3	light	3x/week; 30 minutes	
Week 4	moderate	3x/week; 15 minutes	
Week 5	moderate	3x/week; 30 minutes	
Week 6	moderate	4x/week; 30 minutes	
Week 7	moderate	5x/week; 30 minutes	
Week 8	moderate	5x/week; 30 minutes	

Inclusion criteria:

- Age 21-85 years
- Willing and able to provide informed consent
- New onset of Post ST elevation and non-ST elevation myocardial infarction/staged PCI/ acute coronary syndrome/unstable angina
- Own and able to operate App on smartphone

Exclusion criteria:

- History of ventricular fibrillation not in the setting of acute myocardial infarction
- Documented sustained ventricular or supraventricular arrhythmia
- Unstable angina
- Awaiting staged revascularization
- Inability to perform 6MWT

Block randomization using sequentially numbered sealed envelopes would be used to assign patients to the intervention or control arms.

The primary outcome measure is compliance and adherence to the “Kardia” program. Other endpoints include 6MWT, patient wellbeing and behaviour (e.g. dietary habits, stress levels, physical activity) assessed using questionnaires, major adverse cardiovascular events (MACE), modification of cardiovascular risk profiles (i.e. LDL, BP, BMI, HbA1c, etc) and medicine compliance. The outcome measures and the corresponding measurement tools are listed in Table 1.

Table 1.

Outcome Measures	Measurement Tools
Primary Outcome Measures:	

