Compliance to smart phone based cardiac rehabilitation program	Uploading of completed data (BP, activity) to web portal (90% compliance in intervention group would be considered acceptable)
Adherence to physical activity guidelines (150 minutes of moderate level exercise per week) at months 3 and 9	Questionnaire (a difference of 30% is considered significant)
Secondary Outcome Measures:	
6MWT at baseline (within 2 weeks upon discharge) months 3 (+/- 2 months) and 9 (+/- 3 months)	6MWT
Risk Factors	Blood pressure Blood tests, i.e. lipid profile, HbA1C Body weight/ Body Mass Index (BMI)/ Waist/hip circumference Smoking
MACE or hospitalization	Clinical notes
Medication Compliance	Questionnaire
Overall well being	Questionnaire (EQ5D)
Dietary habits	Questionnaire (FFQ)
Psychosocial well being	Questionnaire (K10, DASS 21)
Additional analyses:	
Reasons for non-compliance	Questionnaire
Smoking status	Questionnaire (SMOKING CESSATION SERVICE QUESTIONNAIRE)
Satisfaction and Usability	Questionnaires for patients and clinical staff in intervention group
Costs	Cost to implement Kardia (Staff-time, project implementation, facility cost)
Predictive analyses for re-hospitalizations, etc	Biofourmis

Sample size calculation

Previous studies have shown compliance of centre-based cardiac rehabilitation programs at about 60%. Based on that assumption, a sample size of 50 patients is necessary to show a 30% improvement in compliance in the mHealth arm, with $\alpha=0.01$ and power of 90%.

Statistical analyses

Data will be expressed as mean \pm SD for continuous variables and medians and IQR for skewed data. Statistical comparisons will be performed using paired Student's t test for within group changes over time, unpaired Students' t test for differences between intervention and control arms. Wilcoxon signed-rank test will be used to compare skewed data. Categorical variables will be expressed as counts and percentages and will be analysed using Chi-square test (or Fisher's exact test). All statistical tests will be 2-tailed and statistical significance will be based on $p<0.05$

Data Collection

Paper case record forms will be prepared. Questionnaire booklets will be provided to obtain patient responses. A research assistant will record the data and the data will be checked by the principal investigator for quality assurance. The data will be entered into an electronic database which will be password protected.

Adverse Event and Serious Adverse Event Reporting

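### The sample size is stated at alpha 0.01 with 90% power, but every planned test is two-tailed at p<0.05, so the stated error rate and power belong to no planned test

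*Combined protocol and SAP*

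**What the plan says.** The Sample size calculation section starts from a reference rate: "Previous studies have shown compliance of centre-based cardiac rehabilitation programs at about 60"%. It concludes that "a sample size of 50 patients is necessary to show a 30% improvement in compliance in the mHealth arm", with alpha set at 0.01 "and power of 90"%. It does not say whether that alpha is one- or two-sided. Methods/Approach puts 50 patients in each arm and does not replace dropouts.

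The next section, Statistical analyses, gives one rule for everything: "All statistical tests will be 2-tailed and statistical significance will be based on" p<0.05. Categorical variables "will be analysed using Chi-square test", with Fisher's exact test as the alternative.

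Table 1 lists two primary outcomes. One is compliance measured by data uploads, where "90% compliance in intervention group would be considered acceptable". The other is "Adherence to physical activity guidelines (150 minutes of moderate level exercise per week) at months 3 and 9", where a 30% difference is the stated criterion. The sample-size paragraph does not say which outcome or month it covers.

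**The concern.** The two adjacent sections give different error rates. Nothing in the protocol links them, for example by dividing alpha between the two primary outcomes. If 0.01 is the design level, the analysis section does not apply it. If 0.05 is the level, the sample-size statement describes a test that will not be done.

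Two things depend on the answer. The first is the decision rule: a between-arm p value of 0.03 meets the threshold in one section and misses the alpha in the other, and this should be settled before data are seen. The second is the tolerance for dropout: no allowance is stated, and the loss that still leaves 90% power depends on the alpha and on the test.

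**Working it through.** **Inputs.** Reference rate 0.60 and improvement 30% (Sample size calculation); 50 per arm (Methods/Approach); chi-square or Fisher, two-tailed, 0.05 (Statistical analyses).

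**Reading the 30%.** I take it as absolute, 0.60 versus 0.90, because Table 1 uses 90% as the acceptable rate. A relative reading (0.60 versus 0.78) needs 170 per arm at one-sided 0.01 and 137 at two-sided 0.05 (pooled formula, 90% power), so it cannot give 50.

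**Reproducing the 50.** With d = 0.30, mean proportion 0.75 and z = 1.282 for 90% power:

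- Unpooled: n = (z_alpha + z_power)² × (0.6×0.4 + 0.9×0.1) / d² = (z_alpha + 1.282)² × 0.33 / 0.09
- Pooled: n = [z_alpha × √(2×0.75×0.25) + 1.282 × √0.33]² / 0.09
- Continuity-corrected: n' = (n/4) × [1 + √(1 + 4/(n×d))]², with n from the pooled formula

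| Alpha | z_alpha | Unpooled | Pooled | Corrected |
|---|---|---|---|---|
| One-sided 0.01 | 2.326 | 47.7 | 51.9 | 58.4 |
| Two-sided 0.01 | 2.576 | 54.6 | 59.5 | 66.0 |
| Two-sided 0.05 | 1.960 | 38.5 | 41.7 | 48.1 |

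Example, one-sided 0.01, unpooled: (2.326 + 1.282)² × 3.667 = 13.02 × 3.667 = 47.7.

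With alpha held at 0.01, about 50 per arm appears only for a one-sided test without continuity correction (48 to 52). Two-sided 0.05 with continuity correction gives 49, so a misprinted alpha would also explain the figure. Two other readings fail. Comparing the mHealth arm alone with a fixed 60% needs only 26 (one-sided 0.01) or 31 (two-sided 0.01) patients. Taking 50 as the total is excluded by the 50 in each arm.

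**Exact power.** For n per arm, sum Bin(i; n, 0.6) × Bin(j; n, 0.9) over all pairs (i, j) whose p value is below alpha. At n = 50:

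| Test level | Chi-square | Fisher |
|---|---|---|
| One-sided 0.01 | 90.3% (score test) | 86.0% |
| Two-sided 0.01 | 84.8% | 79.3% |
| Two-sided 0.05 (planned) | 95.4% | 92.7% |

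**Smallest n per arm with 90% power, same method.**

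- Two-sided 0.05, chi-square: 40 (90.1%; 89.5% at 39). This allows a loss of 10 of 50, or 20%.
- Two-sided 0.05, Fisher: 47 (90.6%; 89.8% at 46). This allows a loss of 3 of 50, or 6%.
- Two-sided 0.01, chi-square: 58 (90.4%; 89.7% at 57).
- Two-sided 0.01, Fisher: 64 (90.3%; 89.9% at 63).

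At two-sided 0.01, 50 per arm is short of 90% even with no dropout. The dropout margins assume equal loss in both arms.

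**The case against.** The strongest reply is that nothing is miscalculated and nothing is lost. The 50 reproduces at one-sided 0.01, and planning at a stricter level than the analysis uses is not invalid. The planned test also exceeds 90% power on the assumed rates, and the shortfall to 85% or 79% arises only if two-sided 0.01 decides the result, which no section says. All of this stands. It makes the point an internal inconsistency rather than an arithmetic slip, and it limits the harm. It does not make the stated alpha and power true of any planned test.

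A second reply is that writing 95% into the protocol would give false assurance. Controls receive no devices or app, so portal uploads cannot be compared between arms. The between-arm primary outcome is activity adherence, for which no control rate is given, and the 60% comes from centre-based programmes. This has force. If the control rate were different (my assumption, since the protocol gives none) and the difference still 30 points, power at two-sided 0.05 with 50 per arm would be:

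- 20% versus 50%, or 50% versus 80%: 89.5% (chi-square), 85.3% (Fisher)
- 30% versus 60%, or 40% versus 70%: 87.6% (chi-square), 82.9% (Fisher)

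So 95% and 93% hold for 60% versus 90%, not for every 30-point difference. The restatement must therefore carry its rates and name its endpoint. That is a condition on the repair and does not remove the need for it.

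**Conclusion.** The concern holds. The protocol states alpha 0.01 with 90% power; its own two-tailed rule gives 84.8% (chi-square) or 79.3% (Fisher) at 0.01, and 95.4% or 92.7% at the planned 0.05. The documents do not settle whether 0.01 was meant as one-sided, as a stricter primary threshold, or is a misprint.

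The error is on the conservative side, and on 60% versus 90% the trial is not underpowered before dropout. The figures rest on 50 evaluable patients per arm, the absolute reading of the 30% improvement, and a 60% control rate that does not come from routine care. It should be fixed, because it leaves open the threshold for a primary comparison and the dropout the design can bear.

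**What to change.** Keep 50 per arm. In Sample size calculation, replace the alpha and power clause with wording such as:

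> Two-sided alpha 0.05, 50 per arm, 60% versus 90% (absolute difference): about 95% power with the chi-square test and 93% with Fisher's exact test. By exact calculation, 90% power is kept with 40 evaluable patients per arm (chi-square) or 47 (Fisher).

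In the same paragraph, name the between-arm primary endpoint and the month to which this applies, and label the 60% as an assumption from centre-based programmes, not from the routine-care arm. If a different control rate is adopted for the named endpoint, recompute the power and the evaluable numbers for it.

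If 0.01 is truly intended for the primary outcome, write two-sided 0.01 for that outcome into Statistical analyses and restate power as about 85% (chi-square) or 79% (Fisher) before dropout.

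Either route costs two or three sentences, with no extra patients and no change to procedures. Keeping 0.01 also means accepting a stated power below 90%.

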Protocol Title: Kardia – A smartphone-based care model for outpatient cardiac rehabilitation

Protocol No: Kardia

Principal Investigator: [name]

Protocol Version 1.1 dated 31 May 2017

Specific Aims and Hypothesis:

This study aims to show that a smartphone-based Cardiac rehabilitation program which provides blood pressure monitors and wearable vital signs monitors is feasible and safe in low risk post-myocardial infarction patients in Singapore.

The hypotheses are as follows:

1. Smart-phone based model for cardiac rehabilitation is safe and will improve adherence to recommendations for physical activity post-myocardial infarction
2. The uptake of this home cardiac rehabilitation would lead to improvement in the following objective outcome measures:
 - a. 6 minute walk tests
 - b. Cardiovascular risk factors
 - i. Blood pressure
 - ii. Blood tests, i.e. lipid profile, HbA1C
 - iii. Body weight/ Body Mass Index (BMI)/ Waist/hip circumference
 - iv. Smoking
 - c. Major Adverse Cardiovascular Events (MACE) and Hospitalizations (12 months)
3. This smart-phone based model will allow patients to play an active role in their own management resulting in improvement in lifestyle habits and quality of life
 - a. Physical activity
 - b. Dietary habits (Dietary Habits Questionnaire)
 - c. Psychosocial wellbeing (Kessler 10 Psychological Distress Scale; Depression, Anxiety and Stress Scale 21)
 - d. Quality of life (EQ5D)
 - e. Compliance to medications
 - f.
4. The program will result in a lasting change in patient behaviour and lifestyle.

Background and Clinical Significance

Cardiovascular disease (CVD) is the most common cause of death in Singapore, accounting for ~34% of deaths. This means 1 in every 3 deaths in Singapore is due to heart disease or stroke. Ischemic heart disease is the leading cause of mortality and accounts for 17% of all deaths attributable to life-style related risk-factors. The total burden of this disease is likely to increase given the aging population and the increase in prevalence of obesity and predisposing conditions such as diabetes mellitus, hypertension and hyperlipidaemia.

A number of modifiable environmental and patient specific factors increase the chance of developing coronary artery disease (1). These include smoking, high blood cholesterol, physical inactivity, diabetes, high blood pressure and obesity. Following myocardial infarction, acute coronary

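### The plan does not say that the between-arm comparison decides hypothesis 2, and that comparison is not adjusted for baseline; for the 6MWT, a within-arm gain could pass for a programme effect

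*Combined protocol and SAP*

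**What the plan says.** The design, under Methods/Approach, is a parallel randomised comparison: "The project is a randomized controlled study of smartphone based cardiac rehabilitation program compared to routine care". Each arm has 50 patients ("50 patients who are randomized to the intervention group (mHealth"; "The control group (50 patients) will just be monitored at fixed intervals"). Dropouts are not replaced.

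Hypothesis 2, under Specific Aims and Hypothesis, reads "The uptake of this home cardiac rehabilitation would lead to improvement in the following objective outcome measures". The list covers 6MWT, blood pressure, lipids, HbA1c, weight and girth measures, smoking, and clinical events. No comparator is named.

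Table 1 lists "6MWT at baseline (within 2 weeks upon discharge) months 3 (+/- 2 months) and 9 (+/- 3 months" as a secondary outcome. The risk factors (for example "Blood tests, i.e. lipid profile, HbA1C") are also secondary, but Table 1 gives no measurement times for them.

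The Statistical analyses section sets out "paired Student's t test for within group changes over time, unpaired Students' t test for differences between intervention and control arms", and for skewed variables "Wilcoxon signed-rank test will be used to compare skewed data", which is itself a paired procedure. Tests are two-tailed at p<0.05. The section does not say:
- which of these tests decides a hypothesis;
- whether the unpaired test compares follow-up values or changes;
- whether baseline enters any model as a covariate.

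**The concern.** Read literally, a hypothesis of improvement is met by a significant paired test in the intervention arm alone. For 6MWT that test starts from a measurement taken shortly after discharge, in patients whom the Background describes as recovering from myocardial infarction and who are followed in cardiology clinics in both arms. The change within one arm is the sum of recovery, routine care, any effect of repeating the test, and the programme. Only the contrast with the control arm isolates the programme, and nothing in the analysis text makes that contrast decisive.

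Two things are at stake. The first is a claim of benefit for walking capacity that the randomised comparison does not support. The second is avoidable imprecision in the comparison that can support one, in a trial of 50 per arm.

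**Working it through.** **Inputs from the documents.** 50 per arm; two-sided 0.05; paired t within arm; unpaired t between arms. The documents give no SD, correlation, expected recovery, target difference or power for 6MWT, so there is no plan figure to reproduce on this point. The stated sample size concerns compliance.

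**Assumptions.** 6MWT SD 80 m at each visit; correlation ρ between baseline and follow-up of 0.6 (range shown); a gain of 20 to 40 m shared by both arms; a true between-arm difference of 40 m (0.5 SD) for the power comparison.

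**Step 1: the paired test with no programme effect.**
SD of change = 80 × √(2(1 − 0.6)) = 71.6 m. Noncentrality = gain ÷ 71.6 × √50, with 49 degrees of freedom.

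| Shared gain | Noncentrality | P(intervention arm significant) | P(intervention significant, control not) |
|---|---|---|---|
| 20 m | 1.98 | 0.49 | 0.25 |
| 30 m | 2.96 | 0.83 | 0.14 |
| 40 m | 3.95 | 0.97 | 0.03 |

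The last column is p(1 − p), because the arms are independent. In SD units, a shared gain of 0.3 SD gives a significant intervention-arm test with probability 0.42, 0.55 or 0.77 at ρ = 0.3, 0.5 or 0.7.

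**Step 2: the between-arm test with no programme effect.** In 20,000 simulated trials with a shared gain of 0.5 SD, at ρ = 0.5 and at ρ = 0.7, the unpaired t test rejected in 0.048 to 0.052 of trials, whether run on follow-up values or on changes. The shared gain cancels. In the roughly 13% of trials where the arms differed at baseline by more than 0.3 SD, the rejection rate was about 0.10 to 0.21. This averages back to 5% over randomisation.

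**Step 3: precision of the between-arm test.** The SD that enters the comparison is:
- follow-up values: 80;
- change scores: 80√(2(1 − ρ));
- ANCOVA: 80√(1 − ρ²).

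Noncentrality = 40 ÷ (SD × √(2/50)). At ρ = 0.6 this is 40 ÷ (80 × 0.2) = 2.50 for follow-up values, 40 ÷ (71.6 × 0.2) = 2.80 for change and 40 ÷ (64 × 0.2) = 3.13 for ANCOVA.

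| ρ | Follow-up values | Change scores | ANCOVA | ANCOVA variance ÷ follow-up | ANCOVA variance ÷ change |
|---|---|---|---|---|---|
| 0.5 | 0.70 | 0.70 | 0.82 | 0.75 | 0.75 |
| 0.6 | 0.70 | 0.79 | 0.87 | 0.64 | 0.80 |
| 0.7 | 0.70 | 0.89 | 0.93 | 0.51 | 0.85 |

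The first three result columns are power. The ratios are 1 − ρ² and (1 − ρ²) ÷ (2(1 − ρ)). All powers assume complete data. With dropouts not replaced, each would be lower.

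**The case against.** The strongest reply is that the trial is randomised, has a concurrent control arm, and already plans a between-arm test. Recovery common to both arms cancels in that test, and chance imbalance is already covered by its 5% error. This stands. A reader might infer that recovery or drug treatment biases the unadjusted between-arm comparison; it does not, and step 2 shows as much. Lack of adjustment costs precision and protection against chance imbalance, not validity.

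Other limits also stand:
- A reader might infer that the baseline is collected and then ignored. The paired tests use it, and the unpaired test may be meant for change scores. The accurate statement is that baseline is not named as a covariate.
- A reader might extend the early baseline to blood pressure, lipids, HbA1c and weight. The timing is documented only for 6MWT. Drug-driven change in those measures is an inference, and since the app gives medication reminders, part of any such change could be an intended programme effect.
- When the shared gain is large, the control arm's paired test will usually be significant too, which would reveal the recovery to anyone who looks. If each arm's test had 80% power, the arms would disagree 2 × 0.8 × 0.2 = 32% of the time, but only half of that, 16%, favours the intervention.
- No text says a within-arm test will decide hypothesis 2, and these are secondary outcomes.

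What does not stand is the idea that the plan already settles the matter. It lists both tests side by side and leaves the choice open.

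**Conclusion.** The point holds as a gap in specification and a loss of precision, and should be corrected before analysis. It does not show that the planned between-arm test is invalid.

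For 6MWT, if the paired test were taken as evidence, the chance of apparent support with no programme effect would be far above 5% over the assumed range of shared gain. The gain from baseline adjustment depends on which unadjusted test was meant: 12, 17 or 23 points of power over follow-up values at correlation 0.5, 0.6 or 0.7, and 12, 8 or 4 points over change scores. The SD, correlation, shared gain and 40 m difference are all assumptions. The direction of both results is less sensitive to them than the size: any sizeable shared gain inflates the within-arm finding, and in large samples ANCOVA has variance no greater than either unadjusted version.

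**What to change.** In the Statistical analyses section:

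1. State that hypothesis 2 is judged only on the difference between the randomised arms.
2. For 6MWT, and for each continuous risk factor with a collected baseline, replace the unpaired t test with a linear model of the follow-up value on arm plus that measure's own baseline, at months 3 and 9. Report the adjusted difference with its confidence interval.
3. Report paired within-arm changes as descriptive only, with no claim of programme effect.
4. State when the risk-factor baselines are taken, since the documents do not.

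The cost is a few sentences of text. For 6MWT no new patients or measurements are needed, because the baseline is already scheduled. For the risk factors the same applies only where a baseline is in fact collected.

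### The only rank test named for skewed data is the paired signed-rank test, which cannot compare two unmatched randomised arms

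*Combined protocol and SAP*

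**What the plan says.** The Statistical analyses section summarises skewed variables by "medians and IQR for skewed data". For t tests it separates two jobs: a paired test for change over time within a group, and an unpaired "t test for differences between intervention and control arms". The next sentence deals with skewed variables and makes no such separation: "Wilcoxon signed-rank test will be used to compare skewed data". No Mann-Whitney (Wilcoxon rank-sum) or other two-sample rank test is named elsewhere.

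Categorical variables have their own rule: "Categorical variables will be expressed as counts and percentages and will be analysed using Chi-square test (or Fisher's exact test").

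Methods/Approach describes two parallel arms of 50 patients each: "Block randomization using sequentially numbered sealed envelopes would be used to assign patients to the intervention or control arms". It adds: "For drop out subjects, there will not be any subject replacement".

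**The concern.** The signed-rank test works on differences within matched pairs. A patient in one arm of this trial has no partner in the other. Block randomisation balances the numbers allocated to each arm; it does not pair patients.

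The skewed-data sentence follows directly on one that covers both within-arm and between-arm comparisons, and it carries no restriction. The natural reading is therefore that it governs the between-arm comparison too, where the test does not fit. If it is meant for within-arm change only, the test is right for that job, but the only between-arm test left for a skewed outcome is the unpaired t test.

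The randomised comparison is the purpose of the trial, and several secondary outcomes in Table 1 could prove skewed, for example the distress scores, "Questionnaire (K10, DASS 21"). As written, the between-arm test for such an outcome could be settled after the data have been seen.

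**Working it through.** The plan gives no figure to reproduce here. The check sets the named test against the design, then sizes the consequences.

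**Inputs from the documents.** 50 patients per arm, unmatched, dropouts not replaced (Methods/Approach); two-sided tests at 0.05 (Statistical analyses).

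**Assumptions.** The documents give no skewness, effect size or dropout rate for these outcomes. The distributions, the shift of 0.5 log-SD and the dropout of 5–30% are assumptions.

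**Step 1: can the test be run between arms?** It needs equal numbers. With 47 values in one arm and 44 in the other, the software returns an error. If each patient drops out independently with probability *d*, the number lost in each arm is binomial(50, *d*), and

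P(unequal arms) = 1 − Σₖ [C(50,k) dᵏ (1−d)⁵⁰⁻ᵏ]², summed over k = 0 to 50.

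| Dropout per arm (assumed) | 5% | 10% | 15% | 20% | 30% |
|---|---|---|---|---|---|
| P(unequal arms) | 0.813 | 0.866 | 0.888 | 0.900 | 0.913 |

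**Step 2: if the arms happen to be equal, is the answer unique?** No. In one simulated log-normal dataset of 50 against 50 (log-SD 1, log shift 0.5), the rank-sum test gave a single p of 0.009. The signed-rank p ranged from 0.0002 to 0.062 over 2,000 arbitrary pairings of the same values. Over many datasets with the assumed shift, two row orders of the same data fell on opposite sides of 0.05 in 10–13% of cases. With no true difference the figure was about 3–4% in the log-normal scenarios.

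**Step 3: power and type I error under each reading.** Simulation with 50 per arm at two-sided 0.05; 10,000 runs for the log-normal rows and 5,000 for the tied score. The tied score is a log-normal (log-mean 1, log-SD 1) minus 1, rounded down and capped to 0–21, with about 38% zeros in controls; its shift is downward.

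| Scenario | Rank-sum | Signed-rank, arbitrary pairs | Unpaired t |
|---|---|---|---|
| Mild skew (log-SD 0.5), null | 4.8% | 5.0% | 5.2% |
| Mild skew, shift 0.5 log-SD | 67.9% | 64.7% | 65.1% |
| Strong skew (log-SD 1), null | 4.9% | 4.9% | 4.5% |
| Strong skew, shift 0.5 log-SD | 67.1% | 61.6% | 51.3% |
| Tied 0–21 score, null | 4.5% | 4.7% | 4.4% |
| Tied 0–21 score, shift 0.5 log-SD | 60.3% | 55.2% | 49.7% |

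Against the rank-sum test, arbitrary pairing loses about 3 to 6 points of power (67.9 − 64.7 = 3.2; 67.1 − 61.6 = 5.5; 60.3 − 55.2 = 5.1). The t test loses about 3 points under mild skew (67.9 − 65.1 = 2.8), 16 under strong skew (67.1 − 51.3 = 15.8) and 11 on the tied score (60.3 − 49.7 = 10.6). All null rejection rates lie between 4.4% and 5.2%.

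**Step 4: what if the choice is left open?** Each test keeps its level when fixed in advance. Reporting the smallest of the three p-values does not: in the log-normal scenarios this rejected in about 8% of null datasets.

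**The case against.** The strongest reply is that the sentence is unclear, not wrong. It names neither comparison. Read as the counterpart of the paired t test it is correct, and the plan is then merely silent on skewed between-arm comparisons. It may also be a slip for rank-sum. In practice the misuse would tend to correct itself: unequal arms stop the test from running, so the analyst is pushed to a two-sample test, and the row-order problem needs exactly equal arms. The larger power losses come from assumed skewness, and the trial is sized on compliance, not on these outcomes.

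Much of this is fair. The power figures are illustrations, the 10–13% row-order disagreement holds only when there is a real effect, and no power stated in the plan is affected. But none of it supplies a between-arm test. Being forced off the written test by an error message is an unplanned departure, with the replacement chosen once the data are in hand. The within-arm reading leaves variables described by medians to a test of means that loses power as skew grows. A rank-sum slip would be cured by the same correction.

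**Conclusion.** The concern holds. The one rank test in the plan does not suit the comparison of independent arms, and no suitable one is named. Followed literally between arms, the rule usually cannot be run (81–91% of the time under the assumed dropout); when it can, its result depends on row order. Restricted to within-arm change, it leaves a valid t test that gives up about 3 points of power under mild skew and 16 under strong skew, both for an assumed shift of 0.5 log-SD.

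The harm is limited. Type I error is not inflated under either reading fixed in advance; the risk comes from choosing afterwards. Only skewed secondary outcomes are exposed. Primary outcomes analysed as proportions fall under the chi-square or Fisher rule and are untouched.

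**What to change.** In Statistical analyses, replace the skewed-data sentence with:

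> Skewed data: Wilcoxon signed-rank test for within-arm changes; Wilcoxon rank-sum (Mann-Whitney) test for differences between arms.

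The cost is one sentence, with no new data and no change in sample size. It should be in place before any outcome data are examined by arm.

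Separately, and as an optional gain in efficiency instead of a correction of this error, outcomes with a collected baseline could be compared between arms by ANCOVA adjusted for baseline. The walk test is one: "6MWT at baseline (within 2 weeks upon discharge) months 3 (+/- 2 months) and 9 (+/- 3 months"). The size of that gain depends on a baseline-to-follow-up correlation that the documents do not give.
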